### 11.2.3. Interim analyses

- **Safety:** To monitor accurately the potential toxicity of radiotherapy associated with durvalumab and tremelimumab, an initial cohort of 5 patients will be treated. If no dose limiting toxicity is observed in  $\geq 2$  of these patients at the end of the treatment, the rest of patients will be treated at full doses. In contrast, if severe toxicity is observed in  $\geq 2$  of these patients, 3 additional patients will be treated. If dose limiting toxicity is seen in one of these additional patients, the therapeutic regimen will be modified in the subsequent ones, administering full doses of durvalumab but discontinuing tremelimumab after the first dose.
- **Efficacy:** The study will be conducted using a Simon “Optimal design” two-stage sequential design. An interim analysis of response will be performed at the end of the first stage, after the treatment of the first twelve patients treated. Six or more responses in the first stage were required for continuation to second stage accrual.

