***Study Assessments and Criteria for Evaluation:***

***Safety Assessments:***

Toxicity of the treatment will be assessed and graded using Common Terminology Criteria for Adverse Events CTCAE v4.03 and the Toxicity criteria of the Radiation Therapy Oncology Group (RTOG) and the European Organization for Research and Treatment of Cancer (EORTC) criteria. Patients will be evaluated weekly from the start until the end of treatment (week 12).

To monitor accurately the potential toxicity of radiotherapy associated with durvalumab and tremelimumab, an initial cohort of 5 patients will be treated. If no dose limiting toxicity is observed in ≥2 of these patients (in observation period of 12 weeks (4 weeks after RT) , the rest of patients will be treated at full doses. In contrast, if severe toxicity is observed in ≥2 of these patients, 3 additional patients will be treated. If dose-limiting toxicity is seen in one of these additional patients during observation period, the therapeutic regimen will be modified in the subsequent ones, administering full doses of durvalumab but discontinuing tremelimumab after the first dose.

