#### **Clinical data**

In Study D4190C00006 various dose combinations have been explored, with doses of tremelimumab ranging from 1 to 10 mg/kg and doses of durvalumab ranging from 3 to 20 mg/kg. Tremelimumab was given on a Q4W schedule whilst durvalumab was explored in both a Q4W and Q2W schedule, with the goal of identifying the dose combination that best optimizes the benefit-risk profile in an acceptable range of PK and

pharmacodynamic values (Scott Antonia, Sarah B 2016).

Patients treated with doses of tremelimumab above 1 mg/kg had a higher rate of adverse events (AEs), including discontinuations due to AEs, serious AEs (SAEs), and severe AEs. Between the 10 mg/kg durvalumab + 1 mg/kg tremelimumab and 10 mg/kg durvalumab + 3 mg/kg tremelimumab cohorts treated at the q2w schedule, the number of patients reporting any AE, Grade 3 AEs, SAEs, and treatment-related AEs was higher in the 10 mg/kg durvalumab + 3 mg/kg tremelimumab cohort than the 10 mg/kg durvalumab + 1 mg/kg tremelimumab cohort. A similar pattern was noted in the q4w regimens, suggesting that, as the dose of tremelimumab increased above 1 mg/kg, a higher rate of treatment-related events may be anticipated. Further, the SAEs frequently attributed to immunotherapy, pneumonitis and colitis, were more commonly seen in cohorts using either 3 or 10 mg/kg of tremelimumab compared to the 1-mg/kg dose cohorts. Together, these data suggest that a combination using a tremelimumab dose of 1 mg/kg appeared to minimize the rate of toxicity when combined with durvalumab. Thus, all combination doses utilizing either the 3 or 10 mg/kg doses of tremelimumab were eliminated in the final dose selection (Scott Antonia, Sarah B 2016).

In contrast, cohorts assessing higher doses of durvalumab with a constant dose of tremelimumab did not show an increase in the rate of AEs. The data suggested that increasing doses of durvalumab may not impact the safety of the combination as much as the tremelimumab dose. Further, safety data between the 10-mg/kg and 20-mg/kg cohorts were similar, with no change in safety events with increasing dose of durvalumab.

In Study D4190C00006, of all treatment cohorts, the cohort of patients treated in the 20 mg/kg durvalumab + 1 mg/kg tremelimumab group had a tolerable safety profile, but still showed strong evidence of clinical activity. No dose-limiting toxicities (DLTs) were reported in this cohort.

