Preliminary clinical activity of the durvalumab and tremelimumab combination did not appear to change with increasing doses of tremelimumab. The 15- and 20-mg/kg durvalumab q4w cohorts demonstrated objective responses at all doses of tremelimumab, and increasing doses of tremelimumab did not provide deeper or more rapid responses.

Efficacy data suggested that the 20 mg/kg durvalumab + 1 mg/kg tremelimumab dose cohort may demonstrate equivalent clinical activity to other dose combinations. Of the 14 patients in this cohort, there were 4 patients (29%) with PR, 4 patients (29%) with SD, and 2 patients (14%) with PD. Two patients were not evaluable for response (Scott Antonia, Sarah B 2016).

Altogether, the data suggested that a 20 mg/kg durvalumab + 1 mg/kg tremelimumab dose combination should be selected for further development.

Refer to the current durvalumab Investigator's Brochure for a complete summary of non-clinical and clinical information on the durvalumab + tremelimumab combination, including safety, efficacy and pharmacokinetics.

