## **Replacement of patients**

It is planned to replace those patients who interrupt the trial in advance (without having completed 12 weeks of treatment) and have not presented dose-limiting toxicity.

Patients who have not been taking durvalumab and tremelimumab for more than 21 days or who discontinue treatment with radiotherapy for more than 2 weeks will also be replaced.

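### The run-in toxicity rule uses two unlinked event terms, and its second step ignores how many of the first five patients had an event

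*Combined protocol and SAP*

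**What the plan says.** The rule appears in the synopsis (Safety Assessments), Section 3.1 and Section 11.2.3. An initial cohort of five patients is treated.

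- **Continue.** If DLT is not observed in at least two of the five, then "at the end of the treatment, the rest of patients will be treated at full doses".
- **Expand.** If severe toxicity is observed in at least two of the five, three more patients are treated.
- **Modify.** "If dose limiting toxicity is seen in one of these additional patients, the therapeutic regimen will be modified in the subsequent ones": durvalumab stays at full dose and tremelimumab stops after its first dose.

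The synopsis sets the window as "in observation period of 12 weeks (4 weeks after RT". Section 11.2.3 says end of treatment, which the synopsis places at the same point: "Patients will be evaluated weekly from the start until the end of treatment (week 12". The two windows therefore agree.

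DLT also decides who is replaced. The paragraph on replacement in Section 6 covers patients who leave early "without having completed 12 weeks of treatment) and have not presented dose-limiting toxicity".

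The supplied text gives no grade, event list or attribution for DLT. Section 6.1.1 describes severe toxicity as G3-4, related to radiotherapy or to its combination with the study drugs. Section 6.1.2 repeats the grade, and Section 10.2.1 labels grade 3 as severe. All three concern the management or grading of individual patients, and none is tied to the run-in.

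**The concern.** This rule decides whether later patients receive two checkpoint inhibitors at full dose together with pelvic radiotherapy. It has two weaknesses.

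First, it expands on one term and modifies on another, without saying whether they are the same event. Two sites could classify the same toxicity differently. The continue clause can also be read as requiring at least two patients without DLT. On that reading, and with one event term, 2 or 3 events in five satisfy both the continue and the expand conditions.

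Second, the first five patients open the second step, but their count plays no part in the decision. With 3, 4 or 5 events in five, three more patients are still treated before any change, and none of three then leads to no modification. A higher total can therefore produce less action. What follows 0 of 3 is implied rather than written.

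**Working it through.** **Inputs.** Cohorts of 5 and 3, the threshold of 2 of 5 and the threshold of 1 of 3 come from Section 11.2.3. The total of 32 (Section 11.3) leaves 32 − 5 = 27 or 32 − 8 = 24 patients after the run-in. The plan states no operating characteristics for this rule, so there is no figure of its own to reproduce.

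The true event rate p with radiotherapy is not documented, so all values of p are assumptions. The nearest figures are without radiotherapy. For the same-dose cohort, Section 1.3.1 says "No dose-limiting toxicities (DLTs) were reported in this cohort". If the size given there ("Of the 14 patients in this cohort") is the denominator, the one-sided 95% upper limit is 1 − 0.05^(1/14) = 19.3%. Section 1.4.2 gives about 13% for related serious adverse events and about 13% for discontinuations due to adverse events. The range used is 13 to 50%.

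**Same total, different action (one event term).**

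| First five | Added three | Total | Current rule |
|---|---|---|---|
| 2 | 1 | 3 of 8 (37.5%) | modify |
| 3 | 0 | 3 of 8 (37.5%) | no modification |
| 5 | 0 | 5 of 8 (62.5%) | no modification |

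**Probabilities.** X is the number of events in the first five, binomial (5, p). One of three is read as at least one, and 0 of 3 as continue.

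- Current rule, full regimen continues: P(X ≤ 1) + P(X ≥ 2)(1 − p)³.
- Modify at 3 or more of 8: P(X ≤ 1) + P(X = 2)(1 − p)³.
- The difference is the one path that changes: P(X ≥ 3)(1 − p)³.

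At p = 0.30: P(X ≤ 1) = 0.528, P(X = 2) = 0.309, P(X ≥ 3) = 0.163 and 0.7³ = 0.343.

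- Current: 0.528 + 0.472 × 0.343 = 0.690.
- Revised: 0.528 + 0.309 × 0.343 = 0.634.
- Difference: 0.163 × 0.343 = 0.056.

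| Assumed p | Continues, current | Continues, revised | 3+ of 5, then 0 of 3 | 3+ of first 5 |
|---|---|---|---|---|
| 0.13 | 0.956 | 0.944 | 0.012 | 0.018 |
| 0.20 | 0.872 | 0.842 | 0.030 | 0.058 |
| 0.30 | 0.690 | 0.634 | 0.056 | 0.163 |
| 0.40 | 0.480 | 0.412 | 0.069 | 0.317 |
| 0.50 | 0.289 | 0.227 | 0.063 | 0.500 |

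The last column is the share of trials in which three further patients receive the full regimen under the current rule but would not under the revised one.

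**Ambiguous continue clause.** P(X = 2 or 3) is 0.44 at p = 0.30 and 0.58 at p = 0.40. Those are the trials in which both conditions hold on the alternative reading.

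**If severe toxicity is broader than DLT.** Let s be the severe rate and d the DLT rate. Today the full regimen continues with probability P(X ≤ 1 at s) + P(X ≥ 2 at s)(1 − d)³. With s = 0.50 and d = 0.30 this is 0.1875 + 0.8125 × 0.343 = 0.466. Using the narrower DLT in both steps, with the 3-of-8 rule, gives 0.634 (table, p = 0.30). A narrow common term would therefore weaken the run-in.

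**The case against.** The strongest case on the other side has four parts.

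1. **Severe is not undefined.** A reader might infer that neither trigger term has a meaning. The documents do not support that: Section 6.1.1 gives a grade and an attribution, and Sections 6.1.2 and 10.2.1 agree on the grade. This stands. The gap is the missing DLT definition and the missing link between the terms.
2. **Harmonising can backfire.** As the last calculation shows, continuation of the full regimen rises from 47% to 63% if the common event is a narrow DLT. This stands and limits the fix.
3. **The effect is small, and the first five are used.** They do gate the second step, so it would be wrong to say that their results are discarded. Only one path changes, in at most about 7% of trials over the assumed range. This stands as a statement of size. It does not remove the inconsistency, which needs no assumed rate.
4. **Later patients are monitored.** A reader might infer that the 24 to 27 patients after the run-in have no protection, because the stage-1 look concerns response only ("An interim analysis of response will be performed at the end of the first stage, after the treatment of the first twelve patients treated"). The documents do not support that. Section 11.2.1 provides weekly and then three-monthly safety analysis. Sections 4.4, 6.1 and Appendix 1 set patient-level rules. Section 10.3.9 requires serious events to reach the sponsor within 24 hours. Sections 14.3 and 14.4 cover termination and ongoing sponsor monitoring. None carries a study-level count, but choosing judgement over a count is a design choice, not an error.

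**Conclusion.** The point holds for the run-in rule itself. DLT has no definition in the supplied text, its relation to grade 3-4 severe toxicity is not stated, and the second step can act less on more toxicity. These findings come from the wording alone.

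The size depends on assumed true rates, a single event term and the implied outcome after 0 of 3. From 13 to 50%, the inconsistent path occurs in about 1 to 7% of trials. Three extra patients are exposed to the full regimen after 3 or more events in five in 2 to 50%. Both are small if the true rate is near the documented 13%, which was observed without radiotherapy and is not a DLT rate.

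The absence of a cumulative toxicity boundary after the run-in is not part of the fault. A boundary would be an optional addition: its limits would be the sponsor's choice, and its benefit would depend on rates that the documents do not give.

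**What to change.** Change Section 11.2.3 and repeat the wording in the synopsis and Section 3.1.

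1. **One event.** Use the same event in both run-in steps and in the replacement rule. Make it no narrower than grade 3-4 toxicity related to radiotherapy or to its combination with durvalumab and tremelimumab, as in Section 6.1.1, within the 12-week window. Reword the continue clause as fewer than 2 of 5 patients having the event.
2. **Cumulative second step.** Modify at 3 or more of 8, and at once if 3 or more of the first 5 have the event. Otherwise continue at full doses. With one event term, 3 of 8 is already the smallest total that can trigger modification, so the threshold is not tightened.

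The cost is one definition and a reworded rule, with no new visits or patients. The downside is 0.956 − 0.944 = 0.012 and 0.872 − 0.842 = 0.030, that is, about 1 to 3 more trials per 100 modified at true rates of 13 and 20%.

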### 11.3. Determination of sample size

The study will be conducted using a two-stage sequential design. Using the assumption that the treatment would be considered ineffective if it had a response proportion similar

to radiotherapy alone (P0: 0.5) but would be of considerable interest if it had a response proportion of 70% or more (P1: 0.7), the sample size requirement is 12 patients for the first stage and 20 additional patients for the second stage. Six or more responses in the first stage were required for continuation to second stage accrual, and 19 of a total of 32 patients treated to consider the study positive. The study was planned to have a type I error of 0.10 and a power of 80%.

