***Statistical Methods and Data Analysis:***

The primary endpoint of the study is pathological response evaluated by biopsy performed via cystoscopy at the end of the treatment. Pathological response is defined as the absence of muscle-invasive bladder cancer at post-treatment biopsy ( $\leq$ cT1). The study will be conducted using a two-stage sequential \_Simon optimal design. Using the assumption that the treatment would be considered ineffective if it had a response proportion similar to radiotherapy alone (P0: 0.5) but would be of considerable interest if it had a response proportion of 70% or more (P1: 0.7), the sample size requirement is 12 patients for the first stage and 20 additional patients for the second stage. Six or more responses in the first stage are required for continuation to second stage accrual. The study is planned to have a type I error of 0.10 and power of 80% one sided test.

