### 3.8. PRIMARY EFFICACY ANALYSIS

Efficacy of durvalumab plus tremelimumab with concurrent radiotherapy in terms of pathological response rate (Response evaluation by cystoscopy 6 weeks after end of RT).

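### The two-stage cut-offs are each one too low: continuing at 6 of 12 and succeeding at 19 of 32 has a one-sided type I error of 0.175, not 0.10

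*Combined protocol and SAP*

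**What the plan says.** Protocol section 11.3 gives every design input: a null response rate of 0.5, taken as that of radiotherapy alone; an alternative of 0.7; 12 patients in stage 1 and 20 more in stage 2. On error rates it says: "The study was planned to have a type I error of 0.10 and a power of 80" per cent. The synopsis, under Statistical Methods and Data Analysis, adds the sidedness: "type I error of 0.10 and power of 80% one sided test". That synopsis section and section 11.2.3 both name the Simon optimal design.

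The interim rule in section 11.2.3 is: "Six or more responses in the first stage were required for continuation to second stage accrual". The same threshold appears in section 11.3 and in three places in the synopsis (Study Design, Statistical Methods and Data Analysis, Sample Size Determination), so it is not an isolated slip.

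The final threshold appears only in section 11.3: "19 of a total of 32 patients treated to consider the study positive".

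Table 8 in section 11.2.2 lists the Simon decision rule as one of the primary analyses, beside a proportion with a 95% confidence interval. SAP section 3.8, the primary efficacy analysis, names the response rate and gives table shells, with no cut-off or decision rule. Nothing in the SAP confirms or corrects 6 and 19.

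**The concern.** Simon designs are normally tabulated by their rejection bounds: stop if responses are at or below r1, and declare the treatment ineffective if the total is at or below r. The tabulated pair is easily misread as the counts needed to pass. Two features of the plan suggest this happened. First, 6 of 12 is 50%, exactly the null rate, so a regimen performing at the null goes on to stage 2. Second, 19 of 32 is 59.4%, which looks low for a one-sided test of 0.5 at the 0.10 level in 32 patients.

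This is a single-arm trial with one primary go/no-go rule. If the rule is looser than stated, a regimen no better than radiotherapy alone is more likely to be called positive than readers are told, and the interim protects fewer patients from an ineffective regimen.

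**Working it through.** **Inputs.** Null rate p0 = 0.5, alternative p1 = 0.7, n1 = 12, n2 = 20, N = 32, type I error 0.10 and power 80% (protocol section 11.3); one-sided, Simon optimal (synopsis, Statistical Methods and Data Analysis).

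**Formula.** Let a1 be the smallest stage-1 count that continues and a the smallest total that succeeds. With X1 ~ Bin(12, p) and X2 ~ Bin(20, p),

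P(positive | p) = Σ over x1 from a1 to 12 of P(X1 = x1) × P(X2 ≥ a − x1).

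Type I error is this sum at p = 0.5; power is the sum at p = 0.7. The probability of early stopping under the null is P(X1 < a1 | 0.5), and the expected sample size is 12 + 20 × (1 − that probability).

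**Step 1: the design behind the stated figures.** A search over all two-stage designs with N from 15 to 45, type I error at most 0.10 and power at least 0.80 gives the smallest expected sample size under the null at n1 = 12, N = 32, r1 = 6, r = 19: type I error 0.0899, power 0.8051, expected N 19.74. Here r1 and r are rejection bounds, so a1 = 7 and a = 20. The stated 0.10 and 80% are therefore met with the protocol's own stage sizes, but only at cut-offs of 7 and 20.

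**Step 2: the rule as written, a1 = 6 and a = 19, at p = 0.5.**

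| x1 | P(X1 = x1) | X2 needed | P(X2 ≥ needed) | Product |
|---|---|---|---|---|
| 6 | 0.22559 | 13 | 0.13159 | 0.02968 |
| 7 | 0.19336 | 12 | 0.25172 | 0.04867 |
| 8 | 0.12085 | 11 | 0.41190 | 0.04978 |
| 9 | 0.05371 | 10 | 0.58810 | 0.03159 |
| 10 | 0.01611 | 9 | 0.74828 | 0.01206 |
| 11 | 0.00293 | 8 | 0.86841 | 0.00254 |
| 12 | 0.00024 | 7 | 0.94234 | 0.00023 |
| Sum | | | | 0.1746 |

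The sum is the type I error. The same sum at p = 0.7 is 0.9092. Early stopping under the null has probability P(X1 ≤ 5) = 0.387, so expected N = 12 + 20 × 0.613 = 24.3.

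**Step 3: each cut-off in turn.**

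| Continue at | Positive at | Type I error | Power | Early stop under p0 | Expected N under p0 |
|---|---|---|---|---|---|
| ≥ 6 of 12 | ≥ 19 of 32 (as written) | 0.1746 | 0.909 | 0.387 | 24.3 |
| ≥ 7 of 12 | ≥ 19 of 32 | 0.1449 | 0.848 | 0.613 | 19.7 |
| ≥ 6 of 12 | ≥ 20 of 32 | 0.1029 | 0.853 | 0.387 | 24.3 |
| ≥ 7 of 12 | ≥ 20 of 32 (Simon optimal) | 0.0899 | 0.805 | 0.613 | 19.7 |
| ≥ 6 of 12 | ≥ 21 of 32 | 0.0538 | 0.764 | 0.387 | 24.3 |

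Among all cut-off pairs with n1 = 12 and N = 32, only 7 and 20 give both a type I error of at most 0.10 and power of at least 0.80. The loss in early stopping, 0.613 − 0.387 = 0.226, is the null probability of exactly six responses in stage 1. With no interim stop at all, 19 of 32 has a type I error of 0.1885, so allowing for the futility stop does not rescue the stated 0.10.

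**The case against.** The arithmetic has no real rebuttal. The objections concern reading, timing and reach.

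- *Nineteen might mean more than 19.* The text does not say so, and the six-or-more interim rule is explicit. Even on that reading the type I error is 0.103, slightly above 0.10.
- *The 95% confidence interval would expose a weak result.* The exact interval for 19 of 32 is about 0.41 to 0.76 and includes 0.5. This helps a reader, but the decision rule is listed separately and is what makes the study positive. The interval does not correct the stated error rate.
- *It is too late to change the interim.* The SAP part is titled as a 2022 manuscript analysis, and its section 3.1 says all 32 patients meet the population definitions, so stage 2 has evidently been accrued. This stands: the stage-1 rule can now only be disclosed. The final criterion and the reported error rate can still be put right.
- *Changing a success threshold after full accrual may be informed by the data.* This also stands. The change needs a dated justification, and the result should be shown against both thresholds.
- *The two cut-offs do not matter equally.* Correct. Moving only the final cut-off takes the type I error from 0.175 to 0.103; moving only the first leaves 0.145. The interim slip mainly costs efficiency.
- *The verdict may not change.* It changes only if stage 1 had exactly six responses or the total was exactly 19. The documents give no results, so this is unknown.

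**Conclusion.** The concern holds. The protocol takes the sample sizes of the Simon optimal design for 0.5 versus 0.7 but uses its rejection bounds, 6 and 19, as passing counts. The written rule has a one-sided type I error of 0.175, about 1.75 times the stated 0.10, and power of 0.909 rather than 80%. The error runs only towards declaring success. It also lowers the chance of stopping early under the null from 0.613 to 0.387 and raises the expected sample size from 19.7 to 24.3. The planned total of 32 is unaffected.

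These figures assume independent patients with a common response probability, 12 and 32 patients in the response denominators, and a binding interim rule. They do not depend on any trial result.

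**What to change.** In the synopsis, section 11.2.3 and section 11.3, state the rule as: seven or more responses among the first 12 patients to continue, and 20 or more among 32 to call the study positive (type I error 0.090, power 0.805). Put the same rule in SAP section 3.8.

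Because the SAP indicates that all 32 patients have been accrued, the sponsor should also:

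- state which interim rule was applied and how many responses were seen in stage 1;
- set the final cut-off at 20 and, if stage 2 was opened under six or more, report the type I error as 0.103 and power as 0.853. These figures belong to the rule followed, whatever the stage-1 count was. The 0.10 level is then narrowly missed; a cut-off of 21 would meet it (0.054) but with power of only 0.764;
- if 19 is kept instead, replace the stated error rates with 0.175 and 0.909;
- date and justify the change, and report the result against both 19 and 20.

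No extra patients are needed. The cost is a wording amendment to the protocol and SAP and a short disclosure in the report. Power stays above 80% under either rule with a cut-off of 20.
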